**Endpoints:**

Primary Endpoint:

Rate of recovery from cold and flu-like symptoms will be determined by quantifying the proportion of patients achieving a daily total symptom severity score of 0 or 1 using an established 12 symptom scoring system with a severity scale ranging from 0-absent to 3-very severe for each symptom (max of 36 points) through seven days of follow-up.

Secondary Endpoints:

1. Rates of patient-reported adverse events including nausea, vomiting, indigestion, worsening of shortness of breath or difficulty breathing, allergic reaction including skin rash, and need to seek medical care (e.g. hospitalization or physician visit) for a suspected study drug related adverse effect
2. Rates of patient-reported days missed from work or school and hospitalization or physician office visit(s) for respiratory viral illness related complications

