### 6.3 MEASURES TO MINIMIZE BIAS: RANDOMIZATION AND BLINDING

Randomization will be performed using an online generator (<http://www.randomization.com>) that assigns study subjects to a single treatment arm using randomly permuted blocks. The investigational drug pharmacist will conduct maintenance of trial randomization codes and appropriate blinding. Double blinding will be used to limit recall and observer bias given the subjectivity of the primary outcome. Opaque, white colored capsules of the same size will be used to prepare both study supplement and placebo capsules to conceal treatment assignment. Serious adverse events requiring medical care that are suspected to be caused from the study drug or an unintentional ingestion of study drug by non-study participants will initiate un-blinding procedures. This will include contacting research pharmacy personnel or their designee by medical staff treating the adverse event. Research pharmacy personnel are available during normal business hours, however, their designee (other MUHC inpatient pharmacists) will be available 24 hours a day, seven days a week. Treating medical staff will be immediately informed of the study subject's randomization assignment by the research pharmacist or their designee for purposes of emergent medical care; recording of the unblinding will be performed by the research pharmacist and notification will be sent to the primary investigator and Independent Safety Monitor within 24 hours. Documentation of an unblinding event will include: identification of participant unblinded, reason for unblinding, date and time of unblinding, how unblinding information was obtained, and which research team member(s) have been unblinded. Study participants will be removed from the study if they experience an adverse event that requires medical care due to complications from worsening respiratory viral illness or study drug. Patients not removed will be contacted daily via telephone visits for seven consecutive days by MUHC emergency department research staff starting the day after enrollment day for collection of primary and secondary outcome data elements. MUHC emergency department research staff are trained technicians autonomous of study teams for purposes of clinical trial and facilitate independent data collection for study endpoints. Following the seven days of follow-up patients will be dismissed from study participation and will be instructed to follow-up with their primary care provider for any future medical needs.

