### 7 STUDY INTERVENTION DISCONTINUATION AND PARTICIPANT DISCONTINUATION/WITHDRAWAL

#### 7.1 DISCONTINUATION OF STUDY INTERVENTION

Discontinuation from study supplement or placebo does not mean discontinuation from the study, and remaining study procedures should be completed as indicated by the study protocol. If a clinically significant finding is identified (including, but not limited to changes from baseline) after enrollment, the investigator or qualified designee will determine if any change in participant management is needed. Any new clinically relevant finding will be reported as an adverse event (AE).

Adverse events necessitating discontinuation from the study including removing patients from follow-up telephone visits for any remaining outcome related data collection include any event that would lead to a patient requiring hospitalization. This includes hospitalization related to a suspected adverse event from study drug resulting in unblinding procedures or for worsening respiratory status. Patient self-discontinuation of study intervention due to intolerance affecting future compliance will allow patients to remain in the study to complete any remaining telephone visits for primary and secondary endpoint data collection. Efforts to promote compliance including reinforcing patients to administer study product two hours following a meal will be employed before discontinuing patients from study intervention, but patient refusal to continue with treatment will be considered a dropout with an attempt to collect remaining telephone visits for completeness of endpoint related data capture.

The data to be collected at the time of study intervention discontinuation will include the following:

- Date of study discontinuation
- Reason for discontinuation
- Number of study days completed prior to discontinuation of treatment/study withdrawal
- Total number of patient-reported doses taken of study drug prior to discontinuation of treatment/study withdrawal

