## 7.2 PARTICIPANT DISCONTINUATION/WITHDRAWAL FROM THE STUDY

Participants are free to withdraw from participation in the study at any time upon request.

An investigator may discontinue or withdraw a participant from the study for the following reasons:

- Pregnancy
- Significant study intervention non-compliance
- If any clinical adverse event (AE) necessitating hospitalization
- Disease progression which requires hospitalization
- If the participant meets an exclusion criterion (either newly developed or not previously recognized) that precludes further study participation

The reason for participant discontinuation or withdrawal from the study will be recorded. Subjects who sign the informed consent form and are randomized but do not receive the study intervention may be replaced. Subjects who sign the informed consent form, and are randomized and receive the study intervention, and subsequently withdraw, or are withdrawn or discontinued from the study may also be replaced.

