# 8 STUDY ASSESSMENTS AND PROCEDURES

## 8.1 EFFICACY ASSESSMENTS

Patients presenting to MUHC emergency department for cold and flu-like symptoms during the study period will be assessed for eligibility by the admitting physician based on protocol inclusion and

exclusion criteria as previously detailed. Standard evaluation and collection of patient overall health status including past medical history, vital signs, physical exam, necessary imaging, and laboratory assessment will be completed as part of routine care associated with the emergency department visit. Patients enrolled into the study will be randomized and provided study drug the same day of their emergency department visit such that patients will not discharge from the emergency department until they have received their study drug and corresponding instructions for study participation. Testing results including COVID-19 status or positive influenza will be communicated via telephone contact to study patients as part of routine care follow-up and in accordance with MUHC emergency department procedures. Patients meeting exclusion criteria following results of study related testing information will be instructed to discontinue study intervention and follow-up with their primary care provider or other non-study related healthcare provider for appropriate management.

Upon receiving study drug and following discharge from the emergency department study subjects will begin self-administering study product as outlined in section 6.1.2 of this protocol the evening of the day of enrollment. Research staff from the MUHC emergency department will begin contacting patients the following day and daily thereafter for a total of seven consecutive days as described in section 1.3 of this protocol. The following data elements are to be collected each day via telephone visits for the efficacy endpoints:

Primary efficacy endpoints:

Symptom	Severity Score 0 – absent, 1- mild, 2- moderately sever, 3 – very severe
nasal drainage	
nasal congestion	
sneezing	
scratchy throat	
sore throat	
cough	
headache	
hoarseness	
muscle ache	
shivering or feverish	
tiredness	
difficulty in concentration	
Total Severity Score (max: 36 points)	

Recovery from cold and flu-like illness defined as daily total symptom severity score of 0 or 1	Yes or No
day 2	
day 3	
day 4	
day 5	
day 6	

day 7	
day 8	

Secondary efficacy endpoints:

Morbidity Event	Yes or No
missed days from work or school number of days	

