#### 9.4.3 ANALYSIS OF THE SECONDARY ENDPOINT(S)

Secondary endpoints are independent of findings from the primary endpoint.

Rates of adverse events will be determined as a percentage of those subjects self-reporting an event compared to the total cohort following seven days of follow-up. Adverse events will be categorically expressed as a single endpoint. Difference in adverse events will be compared using Chi-squared test with incidence rates expressed as percentages. Analysis will be performed based on intention-to-treat. Missing data will be handled by last observation carried forward based on most recent self-reported adverse event (or lack thereof).

Rates of missed days of work or school will be determined as a percentage of those subjects self-reporting a missed day compared to the total cohort following seven days of follow-up. Missed days will be both categorically expressed as a single endpoint with incidence rates expressed as percentages as well as mean days missed with standard deviation. Difference in missed days will be compared using Chi-squared test for categorically expressed missed days (occurrence of any missed day(s) during study follow-up) and student's t-test for mean days missed. Analysis will be performed based on intention-to-treat. Missing data will be handled by last observation carried forward based on most recent self-reported missed day (or lack thereof).

Rates of seeking medical care including physician office visits or hospitalization for worsening respiratory illness will be determined as a percentage of those subjects self-reporting these events compared to the total cohort following seven days of follow-up. A physician office visit or hospitalization for worsening respiratory illness will be categorically expressed as a single endpoint with incidence rates expressed as percentages. Difference in need to seek medical care will be compared using Chi-squared tests. Analysis will be performed based on intention-to-treat. Missing data will be handled by last observation carried forward based on most recent self-reported medical visit (or lack thereof).

---

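### Section 6.3 ends outcome calls at a lower threshold than 7.1 and 7.2 do, the triggering events are themselves secondary endpoints, and LOCF does not repair the lost data

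*Combined protocol and SAP*

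**What the plan says.** **Section 6.3** states, in obligatory terms, that participants are "removed from the study if they experience an adverse event that requires medical care due to complications from worsening respiratory viral illness or study drug". It goes on: "Patients not removed will be contacted daily via telephone visits for seven consecutive days". Removal therefore ends the calls that supply the primary and secondary outcomes.

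**Section 7.1** puts the threshold at admission. Adverse events necessitating discontinuation, with the consequence of "removing patients from follow-up telephone visits for any remaining outcome related data collection include any event that would lead to a patient requiring hospitalization", are the only ones it describes. A participant who stops the product because of intolerance is treated differently: this "will allow patients to remain in the study to complete any remaining telephone visits for primary and secondary endpoint data collection".

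**Section 7.2** is permissive: "An investigator may discontinue or withdraw a participant from the study for the following reasons". Its adverse-event and disease-progression reasons both require hospitalization. It also lets withdrawn participants be replaced.

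**Endpoints.** The synopsis lists among the safety outcomes the "need to seek medical care (e.g. hospitalization or physician visit) for a suspected study drug related adverse effect". Section 9.4.3 analyses "Rates of seeking medical care including physician office visits or hospitalization for worsening respiratory illness" as a single categorical endpoint. Both items are on the daily call forms in 8.1 and 8.2, and 8.3.6 acknowledges that some study endpoints are serious adverse events.

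**Analysis.** Section 9.3 includes all randomized participants. Section 9.4.2 carries forward the last self-reported symptom score. Section 9.4.3 counts participants who self-report a medical visit and carries forward the last such report, including a report of none.

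**The concern.** A rule that stops outcome collection because an outcome has occurred creates missing data that depend on the outcome. Both triggers in 6.3, worsening illness and suspected drug effect, could differ by arm, so the loss could too. Spare sample size covers lost numbers but not this kind of loss.

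The three sections also let two staff members treat the same office visit in opposite ways, each with support from the protocol. What is at stake is the removed person's remaining symptom scores, missed days and later events, and possibly the triggering event itself.

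**Working it through.** **1. The sections side by side**

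| Section | Trigger | Force | Outcome calls |
|---|---|---|---|
| 6.3 | adverse event requiring medical care (viral illness or study drug) | obligatory | end |
| 7.1 | event requiring hospitalization | obligatory (necessitating) | end |
| 7.2 | hospitalization, among other reasons | discretionary (may) | not stated |

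The threshold differs between 6.3 and the other two. The force differs between 7.2 and the other two.

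**2. What LOCF does to a removed participant**

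- Last score above 1: fixed as not recovered, even if recovery would have followed by Day 8.
- Last score 0 or 1, then worsening and removal: fixed as recovered. If recovery is judged at the end of follow-up, as 9.4.2 can be read, each such person who is in fact unwell at Day 8 adds 1/50 = 2 points to that arm's rate. If recovery at any time within seven days counts, as Section 3 can be read, this case does no harm.
- Triggering event self-reported on a call: counted correctly.
- Triggering event known only from a serious adverse event report or the health record: the earlier report of no visit can be carried forward.

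**3. The plan's own figure**

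Section 9.2, with 60% against 30% and two-sided 0.05:

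n = [1.96·√(0.45·0.55·2) + 0.84·√(0.3·0.7 + 0.6·0.4)]² / 0.3² = 41.92, so 42 per arm and 84 in total. This reproduces.

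The same formula solved for power at the enrolled 50 per arm:

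Φ{[0.3·√50 − 1.96·√(2·0.45·0.55)] / √(0.21 + 0.24)} = Φ(1.107) = 86.6%.

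**4. Illustration of the primary effect**

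The documents give no removal rate. The only loss figure is 5% all-cause dropout (9.2), or 2.5 of 50. The assumptions are:

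- 60% and 30% are the Day 8 recovery rates, reached at a constant hazard over seven days.
- Every removed participant has a last score above 1 and would otherwise have recovered at the arm's rate.
- Calls run from Day 2 to Day 8, so removal after the Day 6, 4 or 2 call loses L = 2, 4 or 6 calls.

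Probability of recovering in the lost calls: active 1 − 0.4^(L/7) = 0.230, 0.408, 0.544; placebo 1 − 0.7^(L/7) = 0.097, 0.184, 0.263. The shift in an arm's rate is r·p/50, where r is the number removed in that arm.

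| Case | r | Lost calls | Active shift | Placebo shift | Difference, equal removal | Power, equal | Difference, all active | Power, all active |
|---|---|---|---|---|---|---|---|---|
| A | 1 | 2 | 0.46 | 0.19 | 29.7 | 86.0% | 29.5 | 85.5% |
| B | 2.5 | 4 | 2.04 | 0.92 | 28.9 | 84.0% | 28.0 | 81.4% |
| C | 5 | 6 | 5.44 | 2.63 | 27.2 | 79.9% | 24.6 | 70.6% |

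Shifts and differences are in percentage points. If all removals are in placebo, the difference widens to 30.2, 30.9 and 32.6 points.

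**5. Sensitivity to the time base**

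Section 9.2 words the 60% and 30% as recovery after five days of treatment. Read that way, the constant hazard gives 1 − 0.4^(7/5) = 72.3% and 1 − 0.7^(7/5) = 39.3% at Day 8, and power at 50 per arm is 92.5%. Equal removal then gives 91.9%, 89.9% and 85.7%. The conclusion does not change.

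**The case against.** **The threshold conflict is partly inferred.** Section 6.3 does not name physician visits, and its removal sentence follows text on unblinding for serious events, so a narrower reading is possible. Section 7.1 is the dedicated discontinuation section, and its verb, include, does not make hospitalization the only trigger. This stands as a limit: a reader might infer that every office visit will end follow-up, and the documents do not establish that. But the synopsis, Section 3 and 9.4.3 all use seeking medical care to cover physician visits as well as admission, so the wider reading follows the protocol's own usage and the question is unsettled.

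**On whether removal is mandatory,** a reader might set 6.3 against both later sections. That is not supported: 7.1 is obligatory too, and only 7.2 differs.

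**Existing capture helps in part.** Technicians ask about events at each call, the date and reason of discontinuation are recorded, events are followed to resolution (8.3.4) and discontinuation events are listed (9.4.4). Loss of the triggering event therefore needs an event known to staff but never self-reported, which is possible but narrow. None of this capture supplies the missing daily scores or missed days, and replacement under 7.2 does not restore the outcomes of the person removed.

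**The removal counts and times are assumed.** That is so, and participants removed for worsening illness probably recover more slowly than their arm's average, so the shifts in the table lean high.

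**Conclusion.** The concern holds. The sections disagree on the threshold (6.3 against 7.1 and 7.2) and on the force (7.2 against 6.3 and 7.1), the triggers are secondary-endpoint components, and LOCF does not repair the lost calls.

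Two stronger readings fail. One is that the rule biases the trial against the active product. The direction is open: freezing participants as not recovered lowers the rate in whichever arm loses them, and a low score carried past a later worsening can raise it. The other is that intention-to-treat is breached. The analysis set in 9.3 is intact; the weakness is in what is imputed for some of its members.

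The size is illustrative only. On the assumptions above, equal removal costs between 0.6 and 6.7 points of power (86.6% to 86.0% or 79.9%), and one-sided removal of 5 active participants after Day 2 costs 16.0 points. The primary effect is small unless removal is frequent or unequal. The point should be fixed because the correction is cheap. Confidence is high on the mismatch of wording and lower on how often it would matter.

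**What to change.** 1. Reconcile 6.3, 7.1 and 7.2. Which clinical removal, study-drug or unblinding rule applies is for the sponsor.
2. Separate withdrawal from outcome collection: participants who agree stay on the already scheduled calls to Day 8 after a medical-care event or hospitalization. Section 7.1 already does this for those who stop the product for intolerance.
3. In 9.4.3, count any documented triggering visit or hospitalization as an endpoint event, whether learned by self-report, serious adverse event report or health record.
4. In 9.4.2, add a sensitivity analysis that varies the recovery status of removed participants in both arms. Counting them as not recovered is defensible, but it should be a stated rule and not a by-product of LOCF.
5. Flag scores collected after unblinding and repeat the analysis without them.

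The cost is amendment wording, one case report form field for the source of the event, and a flag for unblinding. The calls and serious adverse event follow-up are already planned. There are two downsides: hospitalized participants are harder to reach, and scores given after a drug-related hospitalization may be unblinded, which item 5 addresses.

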
### 6.4 STUDY INTERVENTION COMPLIANCE

Compliance of study intervention will be assessed by MUHC emergency department research staff via daily telephone visits. Occurrences of non-compliance will be patient-reported and include number of missed doses for any given day during the on-treatment follow-up period.

### 6.5 CONCOMITANT THERAPY

Patients enrolled will be instructed to discontinue any current OTC products that contain any of the components of the study drug to mitigate confounding of treatment effect. Common cough and cold products that do not share ingredients with study drug will be allowed, and daily utilization will be quantified as name and number of products used and doses of each taken daily using a patient 'sick' diary. This strategy will allow standard-of-care treatment via patient directed symptom management using traditional OTC cough and cold medicines, while minimizing bias in evaluation of study outcomes.

#### 6.5.1 RESCUE MEDICINE

The study site and sponsor will not supply OTC cough and cold rescue medication. Obtainment of this type of therapy will be at the discretion of the study participants with the restriction that no product should include any amount of the study supplement individual components of zinc, green tea, or ascorbic acid (vitamin C).

### 7 STUDY INTERVENTION DISCONTINUATION AND PARTICIPANT DISCONTINUATION/WITHDRAWAL

#### 7.1 DISCONTINUATION OF STUDY INTERVENTION

Discontinuation from study supplement or placebo does not mean discontinuation from the study, and remaining study procedures should be completed as indicated by the study protocol. If a clinically significant finding is identified (including, but not limited to changes from baseline) after enrollment, the investigator or qualified designee will determine if any change in participant management is needed. Any new clinically relevant finding will be reported as an adverse event (AE).

Adverse events necessitating discontinuation from the study including removing patients from follow-up telephone visits for any remaining outcome related data collection include any event that would lead to a patient requiring hospitalization. This includes hospitalization related to a suspected adverse event from study drug resulting in unblinding procedures or for worsening respiratory status. Patient self-discontinuation of study intervention due to intolerance affecting future compliance will allow patients to remain in the study to complete any remaining telephone visits for primary and secondary endpoint data collection. Efforts to promote compliance including reinforcing patients to administer study product two hours following a meal will be employed before discontinuing patients from study intervention, but patient refusal to continue with treatment will be considered a dropout with an attempt to collect remaining telephone visits for completeness of endpoint related data capture.

The data to be collected at the time of study intervention discontinuation will include the following:

- Date of study discontinuation
- Reason for discontinuation
- Number of study days completed prior to discontinuation of treatment/study withdrawal
- Total number of patient-reported doses taken of study drug prior to discontinuation of treatment/study withdrawal

